1.2 Intravesical BCG Immunotherapy for NMIBC

BCG for intravesical use is a live attenuated form of *Mycobacterium bovis* and has been approved by the Food and Drug Administration (FDA) of the United States for the treatment and prophylaxis of carcinoma in situ (CIS) of the urinary bladder, and for the prophylaxis of primary or recurrent stage Ta and/or T1 papillary tumors following transurethral resection (TUR) (<https://www.fda.gov/downloads/BiologicsBloodVaccines/Vaccines/ApprovedProducts/UCM163039.pdf>). Per the American Urological Association (AUA) bladder cancer guidelines it is the standard treatment for patients with high-risk NMIBC following a restaging transurethral resection of bladder tumor. Patients with NMIBC have high recurrence rate after intravesical BCG with or without chemotherapy. Standard definitions of post-BCG states may be used to guide clinical decision-making and clinical trial design [5].

BCG failure: Patients with either intermediate- or high-risk NMIBC who received induction intravesical BCG but failure to achieve tumor response. Up to 40% of patients with NMIBC will fail intravesical BCG therapy [6].

BCG unresponsive: Patients have persistent or recurrent high-grade Ta/Tis or T1 bladder cancer after completion of at least induction (≥ 5 doses) and one round of maintenance (or second induction; ≥ 2 doses) intravesical BCG; or tumor recurrent within six months after initial response. Up to 50% patients with NMIBC have tumor progression after the third cycle intravesical BCG therapy [7].

The difficulty with management of NMIBC has resulted in many attempts to improve treatment. For patients with Ta disease, without additional treatment, cancer recurrence occurs in more than 60% and disease progression occurs in more than 20%. Patients with T1 disease may experience recurrence in more than 75% of patients with progression in 35% of patients. Intravesical chemotherapy may delay recurrence, but does not prevent progression. BCG has been shown to reduce disease progression and recurrence while improving survival. The most benefit from BCG is obtained with a complete maintenance course. Response rates can improve from nearly 40% to over 70% [8, 9]. However, very few patients can tolerate a complete full course of maintenance BCG (~16%) [9]. Patients with persistent tumor or post-BCG recurrence may respond to another challenge with intravesical BCG [10]. However,

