2.2.2 Secondary Endpoints

- 6 Month maintenance treatment completion as defined as completion of at least 2 of 3 maintenance treatments within a 5-week period without unacceptable toxicities or disease progression. Disease status will be evaluated based on cystoscopy and urine cytology prior to maintenance therapy.

Patients with persistent or recurrent high-grade disease at 6 Month cystoscopy will be taken off treatment. Low-grade recurrence will be tolerated without treatment interruption.

- 3-month and 6-month complete response (CR) based on negative cystoscopy and urine cytology.
- Recurrence free survival (RFS) at 6 and 12 months, defined as proportion of patients who are alive and free of persistent or recurrent NMIBC based on cystoscopy, cytology and/or biopsy.
- Progression-free survival (PFS) at 6 and 12 months, as defined by time from day of first treatment to first progression to higher grade or stage, including muscle-invasive disease or death from any cause
- Cystectomy-free survival (CFS), defined as time from study initiation to cystectomy or death
- Overall survival, defined as time from day of first treatment to death from any cause

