3.1 Inclusion Criteria

1. Histologically or cytologically documented Non-muscle Invasive Bladder Cancer (NMIBC).
2. Patient with BCG-treated but unresponsive NMIBC (persistent or recurrent defined as tumor lesion present after prior response).
3. An Eastern Cooperative Oncology Group (ECOG) Performance Status score of 0 to 2.
4. Patients who are able to understand and sign the informed consent form.
5. Age \geq 18 years old
6. Ability to comply with protocol
7. Life expectancy $>/=$ 12 weeks
8. Adequate hematologic and end-organ function
 - ANC \geq 1500/ μ L (without granulocyte colony-stimulating factor support within 2 weeks prior to the first dose of study treatment)
 - Platelet count \geq 100,000/ μ L (without transfusion within 2 weeks prior to the first dose of study treatment)
 - Hemoglobin \geq 9.0 g/dL; Patients may be transfused or receive erythropoietic treatment, at least 7 days prior to the first dose of study treatment, to meet this criterion.

- AST and ALT $\leq 2.5 \times$ ULN.
- Serum bilirubin $\leq 1.5 \times$ ULN; Patients with known Gilbert disease who have serum bilirubin level $\leq 3 \times$ ULN may be enrolled.
- INR and aPTT $\leq 1.5 \times$ ULN; this applies only to patients who are not receiving therapeutic anticoagulation; patients receiving therapeutic anticoagulation should be on a stable dose.
- Creatinine clearance $>/= 30$ milliliters per minute (mL/min) (calculated using the Cockcroft-Gault formula)

9. For women of childbearing potential: Negative serum or urine pregnancy test at screening.
10. For both male and female subjects: agreement to remain abstinent (refrain from heterosexual intercourse) or use highly effective contraceptive methods that result in a failure rate of $<1\%$ per year during the treatment period and for at least 30 days after the last dose of study drug

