8.2 Efficacy Evaluation

Cystoscopy and urine cytology will be obtained at screening and at Month 3, 6, 9, and 12. Only frankly malignant cytology will be considered positive and used to determine the need for bladder biopsy and further evaluation. Three-month complete response (CR) rate, 6-month CR rate, recurrence free survival (RFS), cystectomy-free survival (C

FS), and overall survival will be evaluated as the following.

Time to High-Grade Recurrence (TTHGR) is defined as time from date of first treatment to first high-grade recurrence. Patients without a recurrence will be censored at their last cystoscopy date. Those who die without a recurrence are also counted as a recurrence and high-grade recurrence at time of death.

Time to Recurrence (TTR) is identical to TTHGR with the addition that failure with any-grade bladder cancer is considered an event.

Progression-free survival (PFS) is defined as time from date of first treatment to first evidence of muscle invasive bladder cancer, metastatic disease, or death due to any cause. Those without an event are censored at their last valid tumor assessment, or at the last tumor assessment before patient start of the new therapy if a patient has started new anti-cancer therapy.

Complete Response: For the subset of patients with CIS (with or without concomitant Ta or T1 disease) at study entry, a 6-month biopsy is required. A negative biopsy at 6 months will provide evidence of complete response. A +/- 10 day window will be allowed around the disease assessment time point. Patients receiving a second induction will not be required to undergo 6-month biopsy

Duration of Complete Response: For the subset of patients with CIS (with or without concomitant Ta or T1 disease) at study entry who achieve a CR, duration is defined as time from first documentation of CR to time of first high grade recurrence. Patients who remain CR at end of study (EOS) are censored at their last cystoscopy date.

Overall survival (OS) is defined as the duration from the first dose date of the study drug until death due to any cause. Patients who are still alive at EOS are censored on the date they will be last known to be alive. An exploratory analysis to determine OS at EOS will be estimated by the Kaplan-Meier method.

Patient Reported Outcomes:

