5. The following may be considered as exceptions to DLTs: 1.
- a. Grade 3 nausea, vomiting, or diarrhea and Grade 4 vomiting or diarrhea in the absence of maximal medical therapy that resolves in 72 hours.
 - b. Grade 3 fatigue lasting < 5 days.
 - c. Grade 3 hypertension that can be controlled with medical therapy.
 - d. An increase of indirect (unconjugated) bilirubin indicative of Gilbert's syndrome.
 - e. Serum lipase and/or serum amylase CTCAE Grade 3 ≤ 7 consecutive days without clinical signs or symptoms of pancreatitis.

ii. **Definition of DLT Evaluable Population**

1. Patients enrolled in safety lead-in cohort who receive at least 4 doses and complete the DLT observation period (the first 42 days of induction treatment), unless the patient discontinued the study treatment due to a DLT.

8. Antitumor Evaluation

- a. The proportion of patients receiving a complete induction course (at least 5 of 6 treatments of BCG + avelumab within eight weeks of starting treatment) at 3 months and at 6 months will be calculated and a 95% Wilson score confidence interval constructed for the completion rate.
- b. The 3-month and/or 6-month complete response (CR) rates will be summarized as the proportion (and 95% CI) of patients with complete tumor response at month 3 or 6 of study treatment. Patients who remain CR at end of study (EOS) are censored at their last cystoscopy date.
- c. The duration of response will be calculated as time from the date of first response (complete response (CR), partial response (PR), pathological complete response (pCR)) to the first date of non-response. Duration of response will be summarized using the Kaplan-Meier method. Median duration of response with 95% CI will be computed. Results will be presented in tabular and graphic form, as appropriate.
- d. Progression-Free Survival (PFS) at six month and twelve months is defined as the time in months from the first dose of the drug to the date of death or the first documented date of progression, whichever comes first. For patients who did not die and did not have progression, the PFS is censored at the last documented tumor assessment. Survival curve for PFS will be generated using the Kaplan-Meier method. Median PFS with 95% CI will be computed. Those without an event are censored at their last valid tumor assessment, or at the last tumor assessment before patient start of the new therapy if a patient has started new anti-cancer therapy.

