- e. Overall survival (OS) is defined as time in months from first dose of the drug to the date of death. Patients who are still alive at EOS are censored on the date they were last known to be alive. Survival curve for OS will be generated using the Kaplan-Meier method. Median OS with 95% CI will be computed. If overall survival cannot be calculated due to no patient deaths, it will not be reported.
- f. Recurrence free survival (RFS) at 6 and 12 months, defined as proportion of patients who are alive and free of persistent or recurrent NMIBC based on cystoscopy, cytology and/or biopsy. Survival curve for RFS will be generated using the Kaplan-Meier method. Median PFS with 95% CI will be computed. Patients without a recurrence will be censored at their last cystoscopy date.
- g. Cystectomy-free survival (CFS), defined as time from study initiation to cystectomy or death. Survival curve for CFS will be generated using the Kaplan-Meier method. Median PFS with 95% CI will be computed. If CFS cannot be calculated due to not enough patients undergoing cystectomy, it will not be reported.

9. Safety Analyses

a. Adverse Events

- i. Severity of AEs will be graded according to the CTCAE Version 5.0. Adverse events not included in the CTCAE, Version 5.0 must be graded as follows: Mild, Moderate, Severe, Life-threatening, and Fatal according to the following definitions:
 1. Mild: The AE is noticeable to the patient but does not interfere with routine activity.
 2. Moderate: The AE interferes with routine activity but responds to symptomatic therapy or rest.
 3. Severe: The AE significantly limits the patient's ability to perform routine activities despite symptomatic therapy.
 4. Life-threatening: The AE places the patient at risk of death at the time of the event.
 5. Fatal: The AE results in the death of the patient.
- ii. Frequency and severity of adverse events will be tabulated by body system, type and maximum grade. Serious adverse events will be listed.

b. Laboratory Abnormalities

- i. An abnormal laboratory value that is not already associated with an AE is to be recorded as an AE only if any one of the following criteria is met:
 1. an action on the study drug is made as a result of the abnormality
 2. intervention for management of the abnormality is required
 3. at the discretion of the investigator should the abnormality be deemed clinically significant

10. Handling of Missing Data

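### PFS has two event definitions, the SAP's RFS curve as worded censors recurrence-free deaths, and reporting of OS and CFS is conditional on the events seen

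*Protocol*

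**What the plan says.** **PFS.** Protocol 2.2.2, repeated in SAP 2b.iv, takes the event to be "first progression to higher grade or stage, including muscle-invasive disease or death from any cause". Protocol 8.2 takes it to be "first evidence of muscle invasive bladder cancer, metastatic disease, or death due to any cause". SAP 8d runs to the "date of death or the first documented date of progression, whichever comes first"; it neither defines progression nor cites either definition. Its censoring sentence is the one used in Protocol 8.2 and begins "Those without an event are censored at their last valid tumor assessment, or at the last tumor assessment before patient start"; the rest concerns patients who go on to another anti-cancer treatment. Protocol 6.8 separately treats radiation or surgery involving tumor lesions as disease progression.

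**RFS.** SAP 8f describes the endpoint, at its two landmarks of Months 6 and 12, in these words: "defined as proportion of patients who are alive and free of persistent or recurrent NMIBC based on cystoscopy, cytology and/or biopsy". A Kaplan-Meier analysis is then added to that proportion: "Survival curve for RFS will be generated using the Kaplan-Meier method. Median PFS with 95% CI will be computed". It closes by censoring every patient without a recurrence at the last cystoscopy. It gives the curve no start date. Protocol 8.2 has a near-identical censoring rule for time to high-grade recurrence (TTHGR), which time to recurrence (TTR) shares, but follows it with a sentence counting recurrence-free deaths as events.

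**OS and CFS.** SAP 8e says OS will not be reported if it cannot be computed for want of deaths. SAP 8g says the same of CFS if too few patients have had cystectomy, with no threshold, although its own definition makes death a CFS event too. Protocol 10.2 plans Kaplan-Meier curves for OS, CFS, TTR and TTHGR without condition. SAP section 8 has no TTR or TTHGR curve.

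**The concern.** A patient who moves from Ta to T1 has a PFS event under Protocol 2.2.2 and is event-free under Protocol 8.2, so the same data support two different 6- and 12-month PFS rates. An RFS curve that censors deaths overstates survival free of recurrence and can disagree with the RFS proportion in the same paragraph. Rules that decide from the observed events whether OS and CFS appear leave the report incomplete. Adverse event reporting would not fill that gap: it runs to 90 days after the last dose (Protocol 9.1), while survival follow-up runs to 12 months after treatment (Protocol 10.3). None of this touches the primary endpoint, the sample size or the dose decision.

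**Working it through.** **The plan's own figure.** The documents state no expected rate, event count or precision for PFS, RFS, CFS or OS. The one interval they give, a Wilson lower bound of 37.6% for 60% completion with n = 18, reproduces. The centre is (0.60 + 3.8415/36)/(1 + 3.8415/18) = 0.582 and the half-width is 0.206, giving a lower bound of 37.6%. The same n and method are used below, with all 18 patients assumed fully observed.

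**PFS, events side by side.**

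| Occurrence | Protocol 2.2.2 / SAP 2b.iv | Protocol 8.2 |
|---|---|---|
| Rise in grade or stage within NMIBC (for example Ta to T1) | event | not an event |
| Muscle-invasive disease | event | event |
| Metastatic disease | event (higher stage) | event |
| Death | event | event |
| Radiation or surgery on tumor lesions (progression under Protocol 6.8) | not listed | not listed |

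The definitions part on the first row, and the last row is settled by neither. Grade rises should be limited, because Protocol 1.2 describes BCG-unresponsive patients thus: "Patients have persistent or recurrent high-grade Ta/Tis or T1 bladder cancer". Stage rises remain possible, and inclusion criterion 2 states no grade limit. If k patients have only a first-row event, the PFS rates differ by k/18: 1/18 = 5.6 points; 3/18 = 16.7 points. The value of k is an assumption.

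**RFS curve at Month 6.** Let r3 and r6 be recurrences found at Months 3 and 6, with one recurrence-free death between those visits.

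- Death counted: (17 − r3 − r6)/18.
- Death censored at the Month 3 cystoscopy: (18 − r3)/18 × s, where s = (17 − r3 − r6)/(17 − r3).
- Difference: s × [(18 − r3) − (17 − r3)]/18 = s/18.

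| Assumed r3, r6 | Counted | Censored | Difference (points) |
|---|---|---|---|
| 0, 0 | 94.4% | 100% | 5.6 |
| 6, 3 | 44.4% | 48.5% | 4.0 |
| 12, 3 | 11.1% | 13.3% | 2.2 |
| 12, 5 | 0% | 0% | 0 |

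The error is therefore 0 to 5.6 points per such death.

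**RFS curve at Month 12, one illustration.** Assume recurrences at Months 3, 3, 3, 6, 6 and 9, one death at Month 5, and everyone else followed to Month 12. Death counted: 11/18 = 61.1%. Death censored: 15/18 × 12/14 × 11/12 = 65.5%.

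**Re-induction.** Protocol 6.3.2 allows a second induction for persistence at Month 3. A patient persistent at Month 3 and clear at Month 6 is a success in the Month 6 proportion but a failure on the curve if Month 3 persistence is an event: 1/18 = 5.6 points each. SAP 8f does not say which applies.

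**OS with no deaths.** The Kaplan-Meier estimate is 100%. The upper 95% limit for mortality is 3.8415/(18 + 3.8415) = 17.6% (Wilson), or 1 − 0.025^(1/18) = 18.5% (exact). Only the median cannot be estimated. The chance that SAP 8e applies is (1 − q)^18 for a per-patient death probability q over follow-up: 70% at q = 2%, 40% at 5%, 15% at 10%, all assumed values.

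**The case against.** **PFS.** The SAP states one event, in 2b.iv, and 8d is naturally read with it. A reader might infer from the shared censoring sentence that 8d adopts the narrow Protocol 8.2 event, but that sentence fits either definition, so the inference fails. The contradiction lies between two sections of the protocol; in the SAP there is only a missing cross-reference.

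**RFS.** SAP 8f opens by requiring patients to be alive, so counting deaths was probably intended. The curve is a SAP addition, since Protocol 10.2 lists no RFS curve. Both points stand. The censoring sentence still has no exception for death, and Protocol 8.2 shows that such an exception was written where it was wanted.

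**OS.** The case withheld is the favourable one, invoking the rule discloses that nobody died, and Protocol 8.2 calls its OS estimate exploratory. That makes the harm small. It does not make OS incalculable.

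**CFS.** A reader might infer that with no cystectomies and one death SAP 8g would suppress a CFS of 17/18 = 94.4% (Wilson 95% CI 74.2% to 99.0%). The wording does not support this. The rule applies only if CFS cannot be calculated, and a death is a CFS event that makes it calculable. What remains is a trigger with no threshold that names cystectomies and overlooks deaths.

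**TTR.** Once corrected, the RFS curve is largely the TTR curve of Protocol 8.2, so a separate one would add little. TTHGR is the clear omission.

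**Conclusion.** The point holds in three limited parts.

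1. The protocol defines the PFS event in two incompatible ways, and Protocol 6.8 adds a progression rule found in neither.
2. SAP 8f's censoring sentence conflicts with its own definition of RFS, in the curve only. It would be wrong to infer that the 6- and 12-month RFS proportions are biased; they are not affected.
3. SAP 8e and 8g put conditions on reporting that Protocol 10.2 does not have. It would be wrong to infer that they are built to flatter the treatment.

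The sizes above rest on assumed event counts and complete follow-up of 18 patients; the documents give no basis for predicting them. As these are descriptive secondary endpoints that no decision rule uses, the plan should be corrected, but the trial's main conclusions do not depend on it.

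**What to change.** - **PFS:** have SAP 8d cite the SAP 2b.iv / Protocol 2.2.2 event, align Protocol 8.2 with it, and report the narrower version (muscle-invasive disease, metastatic disease or death) as supplementary. Reconcile the Protocol 6.8 progression rule with the PFS definition.
- **RFS:** keep the 6- and 12-month proportions. For the curve, start at first treatment, count death without recurrence as an event, and censor at last cystoscopy only patients alive without recurrence. State how patients re-induced for Month 3 persistence are counted.
- **Other curves:** add TTHGR to SAP section 8, and either add TTR or state that the corrected RFS curve serves as TTR. In SAP 8f and 8g, relabel the medians, now called PFS, as RFS and CFS.
- **OS and CFS:** delete both non-reporting rules. Always give event counts and the Kaplan-Meier estimate with its interval, showing the median as not reached where needed.

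The cost is SAP wording and a protocol alignment needing IRB approval under Protocol 13.5. No new data are required. The RFS curve may look less favourable.

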2.2.3 Exploratory endpoints

- To obtain preliminary data of potential biomarkers that would associate with tumor response from the combination of avelumab and intravesical BCG.
- Avelumab combined with intravesical BCG will improve quality of life in patients with NMIBC.

3 STUDY POPULATION

Target population: Male or female patients must be 18 years of age or older before the screening visit to be enrolled in the study. Patients must have histologic or cytological diagnosis of Non-muscle Invasive Bladder Cancer (NMIBC), and the cancer is BCG-treated but unresponsive (recurrent or persistent). Patients must have an Eastern Cooperative Oncology Group (ECOG) performance status of 0 to 2 and adequate clinical laboratory values.

The following eligibility criteria are designed to select patients; all relevant medical and nonmedical conditions should be taken into consideration to decide if a particular patient is suitable for this protocol

3.1 Inclusion Criteria

1. Histologically or cytologically documented Non-muscle Invasive Bladder Cancer (NMIBC).
2. Patient with BCG-treated but unresponsive NMIBC (persistent or recurrent defined as tumor lesion present after prior response).
3. An Eastern Cooperative Oncology Group (ECOG) Performance Status score of 0 to 2.
4. Patients who are able to understand and sign the informed consent form.
5. Age \geq 18 years old
6. Ability to comply with protocol
7. Life expectancy $>/=$ 12 weeks
8. Adequate hematologic and end-organ function
 - ANC \geq 1500/ μ L (without granulocyte colony-stimulating factor support within 2 weeks prior to the first dose of study treatment)
 - Platelet count \geq 100,000/ μ L (without transfusion within 2 weeks prior to the first dose of study treatment)
 - Hemoglobin \geq 9.0 g/dL; Patients may be transfused or receive erythropoietic treatment, at least 7 days prior to the first dose of study treatment, to meet this criterion.

- AST and ALT $\leq 2.5 \times$ ULN.
- Serum bilirubin $\leq 1.5 \times$ ULN; Patients with known Gilbert disease who have serum bilirubin level $\leq 3 \times$ ULN may be enrolled.
- INR and aPTT $\leq 1.5 \times$ ULN; this applies only to patients who are not receiving therapeutic anticoagulation; patients receiving therapeutic anticoagulation should be on a stable dose.
- Creatinine clearance $>/= 30$ milliliters per minute (mL/min) (calculated using the Cockcroft-Gault formula)

9. For women of childbearing potential: Negative serum or urine pregnancy test at screening.
10. For both male and female subjects: agreement to remain abstinent (refrain from heterosexual intercourse) or use highly effective contraceptive methods that result in a failure rate of $<1\%$ per year during the treatment period and for at least 30 days after the last dose of study drug

